#### **4.2.4 Prior Systemic Anti-Cancer Therapy**

Prior systemic anti-cancer therapy will be summarized by descriptive statistics for FAS and EES. Number and percentage of participants by below categories will be presented (continuous variables below will also be summarized by mean, standard deviation, median, min and max):

- Number of prior lines of systemic therapy (1, 2 and  $\geq 3$  lines)
- Type of prior CPI received
- Type of prior platinum-based treatment received
- Settings of prior systemic therapy
- Best overall response to prior CPI therapy

#### **4.2.5 Prior Procedures for Primary Cancer**

Number and percentage of participants who underwent any prior surgery or procedure for the treatment of the primary cancer will be presented, and summarized by different types of the procedures for FAS.

#### **4.2.6 Prior Radiation Therapy**

Number and percentage of participants who previously received any radiation therapy for the treatment of primary cancer, area radiated, reason for radiation therapy, and reason for radiation therapy discontinuation will be summarized for FAS and EES.

#### **4.2.7 Previous and Concomitant Medications**

Previous medications will be summarized by therapeutic subgroup (ATC 2nd level) and chemical subgroup (ATC 4th level) and preferred WHO name for the SAF. As with previous medication, concomitant medications will be summarized by therapeutic subgroup (ATC 2nd level) and chemical subgroup (ATC 4th level) and preferred WHO name for the SAF.

Participants taking the same medication multiple times will be counted once per medication and investigational period. A medication which can be classified into several chemical and/or therapeutic subgroups is presented in all chemical and therapeutic subgroups.

Previous medications are defined as medications that patients started prior to first administration of study medication. Concomitant medications are defined as any medications that patients took after the first dose of study medication and through 30 days from last dose of study drug. Medications that started prior to first administration of study drug and continued while study drug was given will be counted in both previous and concomitant medications.

#### **4.2.8 Previous and Concomitant Non-Medication Therapy**

Participants with previous and concomitant non-medication therapy and its reason for use will be presented in the listing.

#### **4.2.9 New Anti-Cancer Therapy**

Number and percentage of participants who received any new anti-cancer therapy , types of anti-cancer therapy and the reason for starting the new anti-cancer therapy will be summarized for SAF.

#### **4.2.10 New Radiation Therapy**

Number and percentage of participants who receive any subsequent radiation therapy will be presented, types of radiation therapy and the reason for starting the new radiation therapy will be summarized for SAF.

#### **4.2.11 Extent of Exposure**

The following information on drug exposure will be presented by treatment group for the SAF:

- Descriptive statistics for duration of exposure (months), number of cycles, number of infusions per participant, cumulative dose, planned dose intensity, dose intensity and relative dose intensity.
- Number and percent of participants with dose adjustment and reasons for dose adjustment.
- Number and percentage of participants who were treated at each cycle
- Number of cycles will be categorized per below categories. Counts and percentages of participants in each of these categories will be summarized.
  - less than or equal to 1 cycle
  - at least 2 cycle, less than 4 cycles
  - at least 4 cycles, less than 6 cycles
  - 6 cycles or more
  - Unknown
- RDI will be categorized according to the following categories. Counts and percentages of participants in each of these categories will also be summarized.
  - less than 50%
  - at least 50%, less or equal to 80%
  - greater than 80%
  - Unknown

Duration of exposure (month) = (Last date of exposure – First dose date + 1)/30.4375.

For EV, last date of exposure = (date of initial dose of the last cycle + 28– 1) or death date if death occurred within the last cycle. For participants who are continuing study treatment at data cutoff date, data cutoff date will be used as the last date of exposure.

Number of cycles is the total number of cycles with non-zero dosing.

Cumulative dose is the sum of (total dose administrated) across all days.

Total dose administrated on a dosing day (mg) = final concentration (mg/ml) \* actual volume administrated (ml).

Planned dose intensity (mg/kg/cycle) is the initial dose of EV multiplied by planned number of dosing days per cycle.

For example, participant is planned to receive EV at a dose of 1.25mg/kg on days 1,8,15 of each cycle, the intended dose intensity =  $1.25 \text{ mg/kg} * 3 = 3.75 \text{ mg/kg}$  per cycle.

(Actual) Dose intensity (mg/kg/cycle) is defined as the actual dose of study drug per unit of time that a participant received over the entire treatment period, defined as below:

$$\text{Dose intensity} = \frac{\sum_{i=1}^{NC} \sum_{j=1}^3 (TD_{i,j} / W_{i,j})}{\text{Duration of exposure}/28}$$

Where  $TD_{i,j}$  is the actual total drug administrated at cycle  $i$  day  $j$ ,  $W_{i,j}$  is the body weight of the participant at cycle  $i$  day 1, and  $NC$  is the total number of cycles with non-zero dosing. If the body weight is greater than 100kg, then  $W_{i,j} = 100\text{kg}$ . If there is no dose administrated in a planned dosing day in a cycle,  $TD_{i,j} = 0\text{mg}$ . Here the duration of exposure is in days.

For the purpose of computing actual, planned and relative dose intensity, neither death nor cutoff dates are used in the derivation of duration of exposure.

Relative dose intensity (%) is defined as

$$\frac{\text{Dose intensity}}{\text{Planned dose intensity}} \times 100$$

## 4.3 Primary Endpoint(s) Analysis

### 4.3.1 Definition of Endpoint(s)

The primary endpoint is efficacy variable:

- Confirmed ORR per RECIST V1.1 by IRC
- Selected PK parameters of ADC, TAb and unconjugated MMAE

Objective response rate (ORR) is defined as the proportion of participants with best overall response (BOR) as confirmed complete response (CR) or partial response (PR), per RECIST v1.1. Participants who do not have at least 2 (initial response and confirmation scan) post baseline response assessments will be counted as non-responders.

Best overall response (BOR) is determined once all tumor timepoint response data for the participant is available. Responses recorded after new anticancer therapy or progressive disease (PD), will be excluded from BOR derivation.

Confirmation of CR or PR should occur at the next assessment (not less than 4 weeks following the initial assessment at which CR/PR is observed).

The BOR with confirmation will be derived according to below criteria per RECIST V1.1:

- If a patient has at least two CR and the first and the last CR dates are at least 28 days apart, then the best overall response is defined as confirmed CR

- If a patient has PR and another CR/PR with at least 28 days apart, then the best overall response for this patient is confirmed PR
- For those patients who do not have confirmed CR or PR, if the patient had at least one tumor assessment record of CR/PR/SD which is at least 49 days after date of first dose, then best overall response is defined as SD
- For those patients who do not have confirmed CR, confirmed PR or SD defined as above, but they have a tumor assessment as PD, their best overall response is PD
- Otherwise, best overall response is defined as Not Evaluable (NE) or No Data (ND) for participants without any post-baseline tumor assessment data

#### **4.3.2 Main Analytical Approach**

The primary analysis of efficacy endpoints will be performed using the FAS.

The primary efficacy analysis will be performed by testing the null hypothesis of ORR being less than or equal to 10% against the alternative hypothesis that ORR is greater than 10% at overall 1-sided 2.5% level of significance. The study will be considered successful if the lower bound of the 2-sided 95% exact Clopper-Pearson CI for ORR is greater than 10%, so that the null hypothesis that the ORR is less than or equal to 10% can be rejected. The primary analysis will be done once confirmatory image scan results are available, or have discontinued from study, or had 30 days safety follow-up after PD, whichever comes first.

The confirmed ORR per IRC and its exact two-sided 95% CI will be calculated for the FAS.

In addition, the ORR per IRC will be summarized by the subgroups defined in Section 4.7.1.

Time to response per IRC will be calculated as the time from the first dose of study drug to the first documentation of objective response (CR or PR that is subsequently confirmed).

Time to response per IRC will be summarized for the confirmed responders only, and will be presented together with duration of response by a swimmer plot.

#### **4.3.3 Sensitivity Analysis**

For sensitivity analysis purpose, the planned analysis for primary efficacy endpoint will be performed using EES.

ORR based on BOR regardless of the confirmation will also be calculated to evaluate the impact on ORR due to missing of confirmatory scans or PD after the initial response.

### **4.4 Secondary Endpoint(s) Analysis**

#### **4.4.1 Definition of Endpoint(s)**

The secondary endpoints are:

- Confirmed ORR per RECIST V1.1 per investigator assessment
- DOR per RECIST V1.1 per IRC and per investigator assessment

Duration of response (DOR) is defined as the time from first documentation of objective response (CR or PR that is subsequently confirmed) to the first documentation of PD or to death due to any cause, whichever comes first. DOR will only be calculated for the participants achieving a confirmed CR or PR.

DOOR will be censored as described below:

- If a participant has neither PD nor death, DOOR will be censored at the date of last evaluable radiological tumor assessment.
- If a participant starts a new anticancer treatment before any PD event or death, DOOR will be censored at the date of last evaluable radiological tumor assessment prior to the date of new anti-cancer treatment.

For a participant who is censored, the last evaluable radiological tumor assessment refers to the participant's last radiological tumor assessment where the response is CR PR or SD.

DOOR (in days) will be calculated as: (Date of documented disease progression or death or censoring) – (Date of the first CR/PR) +1.

To apply the cutoff date to DOOR is to exclude tumor assessments, death and anti-cancer therapy date after cutoff date in the analysis.

- DCR per RECIST V1.1 per IRC and per investigator assessment

Disease control rate (DCR) is defined as the proportion of participants with BOR of confirmed CR or confirmed PR or SD, per RECIST v1.1. Definition of BOR is specified in Section 4.3.1.

- PFS per RECIST V1.1 per IRC and per investigator assessment

Progression-free survival (PFS) is defined as the time from the date of first dose of study drug to the date of first documented radiological disease progression (PD) or death due to any cause, whichever comes first. PFS will be censored as the following:

- If a participant has neither PD nor death, PFS will be censored at the date of last evaluable radiological tumor assessment or at the first dose date if no evaluable postbaseline radiological assessment is available
- If a participant starts a new anticancer treatment before any PD event or death, PFS will be censored at the date of last evaluable radiological tumor assessment prior to the date of new anti-cancer treatment.

For a participant who is censored, the last evaluable radiological tumor assessment refers to the participant's last radiological tumor assessment where the response is CR PR or SD.

PFS (in days) will be calculated as: (Date of documented disease progression or death or censoring) – (Date of first dose of study drug) +1.

To apply the cutoff date to PFS is to exclude tumor assessments, death and anti-cancer therapy date after cutoff date in the analysis.

- OS

Overall survival (OS) is defined as the time from the date of first dose of study drug to the date of death due to any cause. For a participant who is not known to have died by

the end of study follow-up, OS is censored at the date of last known alive date or at the analysis cutoff date, whichever is earlier. All dates which can support a participant's survival status (i.e., lab testing date, drug administration date) will be used to derive the last known alive date. Participants with death or last known alive date after the analysis cutoff date will be censored at the cutoff date.

OS (in days) will be calculated as (Date of death or censoring) – (Date of first dose of study drug) +1.

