5.1 Inclusion Criteria

Participant is eligible for participation in the study if all of the following apply:

1. Institutional Review Board (IRB)/Independent Ethics Committee (IEC) approved written informed consent and privacy language as per national regulations must be

obtained from the participant prior to any study-related procedures (including withdrawal of prohibited medication, if applicable).

2. Participant is legally 18 years or older or considered an adult according to local regulation at the time of signing the informed consent form (ICF).
3. Participant has Eastern Cooperative Oncology Group (ECOG) performance status of 0 or 1.
4. Participant must have histologically or cytologically documented urothelial/transitional cell carcinoma of the bladder, renal pelvis, ureter or urethra. Other histologies including adenocarcinoma, squamous differentiation or mixed are eligible.
5. Participant has locally advanced or metastatic disease that is not amenable to curative intent treatment. Participants must have measurable disease at baseline according to RECIST Version 1.1 ([Eisenhauer 2009](#)). Lesions in a prior radiation field must have progressed subsequent to radiotherapy to be considered measurable.
6. Participant must have received prior treatment with PD-1/PD-L1 inhibitor therapy in the locally advanced or metastatic urothelial cancer setting. Participants who received PD-1/PD-L1 therapy in the neoadjuvant/adjuvant setting and had recurrent or progressive disease either during therapy or within 3 months of therapy completion are eligible.
7. Participant who received prior treatment with platinum-containing chemotherapy defined as those who received platinum in the neoadjuvant/adjuvant setting and had recurrent or progressive disease within 12 months of completion or received treatment with platinum in the locally advanced (defined as unresectable with curative intent) or metastatic setting
 - Platinum based chemotherapy may include combination use with a PD-1 or PD-L1 inhibitor.
8. Participant has the following baseline laboratory data. If a participant has received a recent blood transfusion or growth factor, the hematology tests must be obtained ≥ 7 days after any growth factor and ≥ 28 days after any blood transfusion.
 - a. absolute neutrophil count (ANC) $\geq 1.0 \times 10^9/L$
 - b. platelet count $\geq 100 \times 10^9/L$
 - c. hemoglobin $\geq 9 \text{ g/dL}$

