antitumor activity will be based on confirmed objective response assessments as defined by RECIST V 1.1. Participants who do not have at least 2 (initial response and confirmation scan) post-baseline response assessments will be counted as non-responders. Clinical response of CR, PR, SD, or progressive disease (PD) will be determined at each assessment. Response and progression will also be assessed by IRC and investigator independently.

Survival status will be updated every 12 weeks (± 1 week) (calculated from disease progression) until death, study closure, lost to follow-up or withdrawal of consent from study, whichever occurs first.

Participants' clinical data must be available for CRF source verification. Tumor images will be submitted to a central imaging laboratory.

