10.8 Appendix 8: RECIST Version 1.1

Table 1 – Time point response: patients with target (+/- non-target) disease.

Target lesions	Non-target lesions	New lesions	Overall response
CR	CR	No	CR
CR	Non-CR/non-PD	No	PR
CR	Not evaluated	No	PR
PR	Non-PD or not all evaluated	No	PR
SD	Non-PD or not all evaluated	No	SD
Not all evaluated	Non-PD	No	NE
PD	Any	Yes or No	PD
Any	PD	Yes or No	PD
Any	Any	Yes	PD

CR = complete response, PR = partial response, SD = stable disease, PD = progressive disease, and NE = inevaluable.

Table 2 – Time point response: patients with non-target disease only.

Non-target lesions	New lesions	Overall response
CR	No	CR
Non-CR/non-PD	No	Non-CR/non-PD ^a
Not all evaluated	No	NE
Unequivocal PD	Yes or No	PD
Any	Yes	PD
CR = complete response, PD = progressive disease, and NE = inevaluable. a ‘Non-CR/non-PD’ is preferred over ‘stable disease’ for non-target disease since SD is increasingly used as endpoint for assessment of efficacy in some trials so to assign this category when no lesions can be measured is not advised.		

Response Evaluation Criteria in Solid Tumors

Term	Definition
Complete response (CR)	Disappearance of all target lesions. Any pathological lymph nodes must have reduction in short axis to <10 mm.
Partial response (PR)	A ≥30% decrease in the sum of diameters of target lesions, taking as reference the baseline sum diameters.
Progressive disease (PD)	At least a 20% increase in the sum of diameters of target lesions, taking as reference the smallest sum on study (this includes the baseline sum if that is the smallest on study). In addition to the relative increase of 20%, the sum must also demonstrate an absolute increase of at least 0.5 cm. The appearance of one or more new lesions is also considered progression.
Stable disease (SD)	Neither sufficient shrinkage to qualify for PR nor sufficient increase to qualify for PD, taking as reference the smallest sum diameters while on study.
Measurable lesion	Must be accurately measured in at least one dimension (longest diameter in the plane of measurement is to be recorded) with a minimum size of 10 mm by CT scan (CT slice thickness no greater than 5 mm). A lymph node must be ≥15 mm in short axis when assessed by CT scan to be considered measurable.

From RECIST Version 1.1 ([Eisenhauer 2009](#))

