## **4.10 Sample Size Determination**

Up to 40 participants will be enrolled to study of which approximately 12 participants will be enrolled to the PK cohort. Additional participants may be enrolled in the PK cohort to compensate for participants who become unevaluable for the PK relevant primary endpoint.

The study was designed to estimate the confirmed ORR in participants receiving enfortumab vedotin and to detect an improvement in the ORR compared with a historical 10% response rate which was previously applied in the study EV-201(Cohort 1). The Study EV-201 (Cohort 1) was the pivotal study led to the US registration approval for the same patient population, of which the primary efficacy outcome was 44% ORR with 95% confidence interval (CI) of (35.1%, 53.2%).

The study sample size was determined to detect the ORR improvement of 25% from 10% with sufficient statistical power. The power for various sample size were listed in following table:

Sample Size	Approximate Power Based on Exact Method to Detect a 25% Increase in ORR from 10%
N=30	87%
N=35	95%
N=40	97%
N=50	99%

Therefore, 35 – 40 sample size will be appropriate to have sufficient statistical power to detect the 25% improvement of ORR from 10%.

Up to 40 participants will be enrolled in this study to ensure collection of sufficient efficacy and safety data. Using the estimate of up to 40 participants, the study will have over 97% power to detect a 25% increase in ORR from 10% to 35%, at one-sided significant level of 0.025, based on exact methods.

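### PFS per IRC: a participant read by the IRC as having non-target disease only is censored at first dose while event-free, because Non-CR/Non-PD is not among the evaluable responses

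*SAP*

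**What the plan says.** **Entry and reading.** Protocol 5.1 requires measurable disease: "Participants must have measurable disease at baseline according to RECIST Version 1.1". Neither document requires the IRC to confirm this. Protocol 7.1 adds: "Response and progression will also be assessed by IRC and investigator independently". The FAS (SAP 3.1) keeps every dosed participant, with no exclusion for lack of IRC-measurable disease.

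**Response categories.** Protocol Appendix 8 (10.8), Table 2, covers "patients with non-target disease only". Its possible overall responses are CR, Non-CR/non-PD, NE and PD. PR and SD are not among them, and the footnote advises against assigning SD when nothing can be measured.

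**SAP rules.** The term Non-CR/Non-PD does not appear in the SAP.
- BOR (4.3.1): where no response was confirmed, SD is assigned under this condition: "if the patient had at least one tumor assessment record of CR/PR/SD which is at least 49 days after date of first dose". Failing that, a PD record gives PD. Everything else is NE, or ND if there are no post-baseline data.
- PFS (4.4.1): without PD or death, PFS is censored at the last evaluable radiological assessment, or at the first dose date if there is none. Evaluable is defined by the "last radiological tumor assessment where the response is CR PR or SD".
- PFS when new anticancer therapy precedes PD or death: censored at the last evaluable assessment before that therapy. No alternative date is given if none exists.

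**The concern.** Measurability turns on thresholds in Appendix 8 (10 mm by CT, 15 mm short axis for nodes) and on whether irradiated lesions have since progressed (Protocol 5.1). Two independent readers can differ on these. If the IRC finds no measurable lesion in a participant whom the site enrolled properly, each non-progressing IRC scan short of CR is Non-CR/Non-PD. That is a readable scan showing no progression, yet the SAP does not treat it as evaluable.

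The loss is one-sided. Event-free time is discarded, but an IRC PD or a death in the same kind of participant is kept at its true date. Censoring then depends on outcome, and the Kaplan-Meier estimate of PFS per IRC is pulled down. Calling someone with repeated readable scans Not Evaluable also misdescribes the data.

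**Working it through.** **The plan's own design figure.** SAP 4.10 gives about 97% power at N=40 for ORR 10% against 35%, "at one-sided significant level of 0.025, based on exact methods". The smallest r with P(X ≥ r | 40, 0.10) ≤ 0.025 is r = 9, with exact alpha 0.0155. P(X ≥ 9 | 40, 0.35) = 96.97%, which agrees with the tabulated 97%. This point does not depend on that figure: a participant with only Non-CR/Non-PD scans is a non-responder under any handling.

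**Step 1: apply the SAP rules literally.** Take a participant whom the IRC reads as non-target only, scanned every 8 weeks to Day 336 and every 12 weeks thereafter (Days 420, 504, 588). That is nine scans, with days counted from first dose. PFS in days = event or censoring date − first dose date + 1.

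| IRC course | BOR | PFS per IRC |
|---|---|---|
| Non-CR/Non-PD at all nine scans, no PD, death or new therapy | NE | censored, 0 + 1 = 1 day |
| Non-CR/Non-PD, then PD at Day 420 | PD | event, 420 + 1 = 421 days |
| Non-CR/Non-PD, then death at Day 400 | NE | event, 400 + 1 = 401 days |
| Non-CR/Non-PD at Day 56, CR at Days 112, 168, 224 | CR | censored, 224 + 1 = 225 days |
| Non-CR/Non-PD, new therapy before PD or death | NE (if no later PD is counted) | date undefined |

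The first row stays at 1 day however long follow-up lasts. Once Non-CR/Non-PD counts as evaluable, it becomes 588 + 1 = 589 days. The three event or CR rows keep the same PFS.

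**Step 2: effect on the curve (illustration).** Assumptions: N=40; exponential PFS with median 5 or 8 months; follow-up uniform from 6 to 18 months; k participants read as non-target only, none with CR or new therapy; 1,500 simulated trials per row. The 8 months matches the time to progression anticipated in Protocol 1.1. The 5 months, the follow-up and k are not in the documents.

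| True median (months) | k | 12-month PFS, actual censoring date | 12-month PFS, SAP rule | Fall (points) | KM median (months), actual → SAP rule |
|---|---|---|---|---|---|
| 5 | 1 | 0.188 | 0.184 | 0.4 | 4.81 → 4.81 |
| 5 | 2 | 0.189 | 0.182 | 0.7 | 4.78 → 4.78 |
| 5 | 4 | 0.187 | 0.173 | 1.4 | 4.83 → 4.83 |
| 5 | 6 | 0.190 | 0.169 | 2.1 | 4.88 → 4.83 |
| 8 | 1 | 0.352 | 0.347 | 0.5 | 7.80 → 7.77 |
| 8 | 2 | 0.356 | 0.345 | 1.1 | 7.90 → 7.77 |
| 8 | 4 | 0.352 | 0.330 | 2.2 | 7.84 → 7.61 |
| 8 | 6 | 0.357 | 0.323 | 3.4 | 7.90 → 7.44 |

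**Step 3: DCR, only if the sponsor counts this category.** Each participant whose BOR becomes Non-CR/Non-PD moves DCR per IRC by 1/40 = 2.5 points. For an assumed 0 to 4 participants the range is 0 to 4/40 = 10 points.

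**The case against.** The strongest reply is that the trigger is not shown to occur. Measurable disease is an entry criterion, Protocol 5 bars eligibility waivers, and Protocol 7.1.4 frames overall response for participants with measurable disease at baseline. Table 2 of Appendix 8 is reproduced from RECIST 1.1 and does not show that the case is expected. Handling of a read without target lesions may sit in the IRC charter (Protocol 10.1.5), which is a separate document not reviewed here. All of this stands as a limit on frequency. It does not close the gap, because the SAP refers to no such mapping and the FAS would keep the participant.

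A reader might also infer more than the text supports:
- *That every such participant loses all progression-free time.* This is not so. PD and death count at their true dates, a CR scan is evaluable, and under new therapy the date is undefined, not Day 1.
- *That DCR per IRC is wrong.* Protocol 9.4.2.2.2 also limits DCR to CR, PR or SD, and Appendix 8 discourages assigning SD here. Leaving these participants out follows the protocol's wording.
- *That the concordance table shows a false mismatch.* The formula in SAP 4.4.2.5 adds matched responders and matched non-responders. IRC NE against investigator SD is a matched non-responder pair. Only the lead-in sentence, which speaks of matching BOR, is loose.

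Finally, PFS per IRC is an untested secondary estimate, and OS is untouched. That limits the importance of the point but does not remove the error.

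**Conclusion.** The point holds for PFS censoring and BOR labelling. As written, an event-free participant whom the IRC reads as non-target only, with no CR scan and no new anticancer therapy, has PFS per IRC of 1 day and BOR NE despite readable scans. Comparable participants with PD or death contribute their full time as events, so the bias is downward.

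The number affected is unknown and may be zero; 0 to 4 of 40 is an assumption. With 1 to 4 affected, the illustration puts the fall in 12-month PFS at about 0.4 to 2.2 points and in the median at 0 to about 0.2 month. With 6, these reach 3.4 points and about 0.5 month. The confirmed-ORR test and its success criterion do not change. This is a minor correction, worth making because the stated rule gives a wrong result whenever the case arises.

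**What to change.** 1. In SAP 4.4.1, define the last evaluable assessment for PFS censoring as CR, PR, SD or Non-CR/Non-PD.
2. In the same section, give the new-therapy rule a stated date for participants with no evaluable assessment before that therapy.
3. In SAP 4.3.1, report Non-CR/Non-PD as its own BOR category instead of letting it fall to NE.
4. State whether that category counts in DCR. This is the sponsor's choice. Counting it would extend the protocol's CR, PR or SD definition and should be declared as such.

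The cost is a few phrases in the SAP and a small programming change. No new data are needed. If the IRC charter already maps this category, the SAP should cite that rule and agree with it.
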